WE CHATT: A Pilot Study to Improve Physician-Youth Communication and Medical Decision Making

NCT05835063

Date of IRB Approval: April 6, 2023

WE CHATT: A PILOT STUDY TO IMPROVE PHYSICIAN-YOUTH COMMUNICATION AND MEDICAL DECISION MAKING

BACKGROUND

Prevalence and Impact of Pediatric Heart Failure. Congenital heart disease (CHD), the most common birth defect, impact 1 in every 100 live births.^{36,37} Due to significant medical advancements, many children born with CHD now survive into adolescence and beyond. In 1985, CHD patients were on average 11 years old. In 2000, the mean age had increased to 17 years old.³⁸ For the growing population of adolescents and young adults (AYAs; 12-24 years) with congenital and acquired heart diseases, survival comes at a cost. Common complications, including heart failure and arrhythmias, require intensive, long-term medical care which has a significant financial impact on society. An estimated 6 billion dollars are spent each year on CHD-related acute care costs,³⁹ accounting for some of the highest resource utilization among all hospitalized children. Approximately 14,000 children experience heart-failure related hospitalizations annually in the US, and the average length of admission has increased over the past two decades. Among this group, 7% die during their hospitalization – a mortality rate nearly 20 times greater than that among children without heart failure and approximately double that in adult heart failure.²⁷ For those with advanced heart failure, ventricular assist device therapies and heart transplantation offer potential for extended survival. However, 1/10 heart transplant recipients will die within a year of transplant.²⁸ For patients with implanted ventricular assist devices as a bridge to transplant or destination therapy (i.e., life-extending intervention for patients who do not meet criteria for transplantation), mortality and morbidity are significant with high rates of stroke, bleeding and sepsis.³³ In PI's study of medical decision making preferences among AYAs pre-heart transplant or post-transplant with serious complications, 6/16 eligible participants (38%) died before study enrollment/completion. Young people who die of heart failure overwhelmingly do so in intensive care settings.³⁰ Rates of hospital-based deaths accompanied by costly and invasive interventions near the end of life are exceedingly higher in pediatric heart failure populations when compared to other illness groups with similar disease severity. For example, more than 50% of youth with progressive cancer die at home. Of those with cancer who died in hospital settings, 45% received mechanical ventilation within the last 24 hours of life⁴⁰ compared to 86% of youth who died of heart disease.³⁰

Palliative and End of Life Care in Heart Failure. The 2014 Institute of Medicine (IOM) report, Dying in America: Improving Quality and Honoring Individual Preferences Near End of Life,²⁹ highlighted a critical need for “increased understanding of ways to improve participation in effective advance care planning and shared decision making among patients and families, including seriously ill children and adolescents, who may be able to participate actively in their health care decision making throughout their lives and as they approach death, and receive medical and related social services consistent with their values, goals and informed preferences.” Research on the end of life and palliative care needs of the growing AYA heart failure population is very limited.³⁰⁻³² Youth with heart failure are also less likely to receive palliative care services when compared to other serious illness populations.³⁵ The lack of research and clinical attention to the palliative and end of life care needs of this young population is significant given high rates of mortality and symptom burden. In a randomized controlled trial of adults with heart failure, palliative care involvement was associated with patient improvements in quality of life and spiritual well-being and decreases in symptoms of anxiety and depression.⁴¹ Others have noted palliative care involvement to be associated with improved patient and family satisfaction, enhanced communication with medical providers, increased access to community and social supports, and reduced medical costs.⁴² As such, it has been recommended that interdisciplinary supportive care be provided throughout the heart failure course with early engagement in advance care planning (i.e., discussing one's wishes

and surrogate decision maker if unable to engage in medical decision making) due to challenges with prognostication and risk of sudden death in heart failure populations.⁴³

Communication in Heart Failure. Despite consensus statement⁴³ and other professional guidelines that recommend all adults with CHD participate in advance care planning,⁴⁴ minimal prognostic, advance care planning and end of life care focused communication occurs across heart failure populations. Among adults with CHD, only 1% recalled discussing advance care planning with their medical team even though 78% of the participants believed their healthcare providers should initiate end of life decision making discussions early in the disease course.⁴⁵ Only 37% of family members of adults who died of heart failure were aware of their loved one's poor prognosis. Few were informed of the imminent death of their family member; as such, over 1/3 of the patients died alone.⁴⁶ Communication about end of life care preferences occurs even less frequently among pediatric heart failure populations. Study PI recently conducted an international survey of multidisciplinary pediatric heart failure providers. Initial data analysis of 82 respondents suggests that providers rarely or never discuss death/dying, advance care planning or prognosis with pediatric patients with heart failure/heart transplant (ages 4-24 years). Respondents indicated a high level of discomfort in discussing these topics and noted that additional barriers include the patient/parent(s) being unaccepting of the prognosis, the patient/parent(s) having unrealistic expectations for treatment, and there being an unknown prognosis/disease trajectory. These barriers should not prevent us from addressing the end of life care needs of our AYA patients and families. Yet, the majority of AYAs with serious illnesses report feeling inadequately informed and insufficiently involved in their health care.^{47,48} Studies in other illness groups suggest that AYAs desire prognostic information early in their disease course. Many want to be made aware of their options and engage in shared decision making with caregivers.^{49,50} Although the degree to which youth desire active participation in discussions about death and dying varies, the majority of AYAs with life-threatening illnesses describe a preference to discuss their end of life care wishes – and to do so prior to becoming acutely unwell.⁵¹ In a randomized controlled trial of a family-centered advance care planning intervention among AYAs with cancer, intervention group family participants reported increased understanding and awareness of AYA end of life wishes.⁵² This is important given that others have documented discordant end of life care preferences among AYAs and their parents.⁵¹ In addition, AYAs in the intervention group were more likely than controls to object to invasive interventions at end of life.⁵² In a similar intervention trial among young people with HIV, engagement in advance care planning was associated with increased positive emotions following the discussion and reduced decisional burden.^{53,54} Others have suggested that youth engagement in advance care planning is associated with increased likelihood of home death and reductions in invasive interventions at end of life.⁵⁰ To the best of our knowledge, no studies outside our pilot work have sought to understand the palliative and end of life care needs of AYAs with heart failure.

STUDY AIMS

Based upon previous research by [name] (PI) and her study team ([HUM00157016](#)), this study will pilot a physician-directed communication focused intervention, WE CHATT. The development of WE CHATT was informed by patients and their caregivers, with the ultimate goal of improving patient-centered communication for young people with advanced heart disease. The primary outcome of this pilot study is determining feasibility and acceptability, however, in the future, WE CHATT aims to (1) improve patient-centered communication with young people with advanced heart disease and (2) increase physician comfort in communicating with young people themselves regarding their communication needs and preferences.

METHODS

Recruitment and Sample

Physicians. A total of 20 physicians will be recruited. 10 will be randomized to participate in the intervention arm and 10 will be randomized to the control arm. Physician participants will be recruited from the Division of Pediatric Cardiology at the University of Michigan, which is currently comprised of 37 attending physicians and 16 fellows. All physicians with dedicated clinical effort will be eligible. Eligible physicians must anticipate remaining on staff ≥ 1 years. Study PI ([name]) and Co-I ([name]) will co-lead recruitment efforts via presentation(s) of study objectives and procedures at faculty/fellow meetings. Cardiology faculty and fellows were informally surveyed regarding interest in participating in the study. Over 90% of faculty and fellows expressed openness to participating in the study. Thus, the recruitment goal of 20 physician participants is feasible.

Patient/Caregivers. Patients (12-24 years) with heart failure symptoms meeting criteria for New York Heart Association (NYHA) Class II - IV heart failure will be eligible (i.e., limitations in physical activity, fatigue, palpitations, dyspnea). One parent/caregiver of patient participants meeting inclusion criteria will also be eligible. This patient age range was selected in accordance with research in other illness groups,^{48,49,51} is consistent with the World Health Organization's definition of adolescent/young adult (AYA), and fulfills the Institute of Medicine's need for research on AYA end of life care preferences and decision making involvement.²⁹ This age range also captures the average age (17 years) of patients with congenital heart disease.³⁸ A *new patient* meeting the above criteria in any hospital setting (inpatient, outpatient cardiology clinic, emergency room) being cared for by a participating physician will be eligible for the study. Patients with significant cognitive/developmental delay with potential to impact study participation will be excluded from the study due to the focus on physician-youth communication. Parents and parent/caregivers who are non-English speaking will be excluded from this pilot study.

Compensation for Time. Intervention arm physician participants will receive a \$100 gift card for their time to complete surveys, attend intervention training, and engage in intervention with patient participants. Control arm physician participants will receive a \$25 gift card for their time completing surveys. All patient and parent/caregiver participants will receive a \$25 gift card for their time completing surveys.

Procedures

Intervention Arm. The WE CHATT communication-tool was developed based upon mixed-methods research and stakeholder engagement (patients, parents, physicians, nurses, hospital leadership) led by study PI, [name], over the past decade. It involves the collaborative completion of a 2-page communication preferences document between a primary physician and an adolescent/young adult patient. Intervention arm physicians will participate in a 1-hour training led by study PI, [name], featuring didactic, multimedia, and experiential-based learning to support their facilitation of the WE CHATT intervention with patients.

Control Arm. Physicians randomized to the control arm will not receive training in the WE CHATT communication intervention. Usual/standard care will be provided.

Descriptive Measures. All physician participants will be asked to complete a background/demographic questionnaire (e.g., age, years of practice, previous communication training). Baseline and post-intervention completion of a previously used/published measure of physician comfort in communicating with patients and families, particularly around difficult topics (i.e., prognosis), will also be completed. Medical chart review will be completed to gather patient demographics and basic medical history, which will be used to define the study sample.

Outcome Measures.

Physician Measures. Intervention-arm physician participants will complete an investigator-designed Likert-rating and open-ended question survey assessing intervention satisfaction, ease of intervention administration/completion, time to complete WE CHATT intervention with patient, barriers/feedback specific to WE CHATT, and knowledge gained/perceived impact on practice.

Patient/Caregiver Measures. Intervention-arm patient and caregiver dyads will complete an investigator-designed Likert-rating and open-ended question survey assessing intervention satisfaction, ease of intervention administration/completion, time to complete WE CHATT intervention with physician, barriers/feedback specific to WE CHATT, and knowledge gained/perceived impact on their medical care. All participating patients and parents will complete the self-administered 18-item Service Evaluation Questionnaire⁴⁹ as an assessment of healthcare satisfaction, which has been used in similarly aged samples.⁵⁰ Patient and caregiver versions of previously validated survey tools of trust in physician (PediTIPS) and perceived empathy (CARE measure) will also be completed.

Analysis Plan. Paired samples T-Test will be employed within the intervention arm to compare mean physician comfort, mean patient/family satisfaction, mean trust in physician, and mean perceived empathy. ANCOVA will be used to examine group differences in physician comfort, patient/family satisfaction, trust in physician, and perceived empathy. Frequencies, percentages and means will be calculated to describe physician, patient and family satisfaction with the WE CHATT intervention.

LIMITATIONS

Non-English speaking participants will be excluded from Study 1, limiting examination of cultural influences on end of life care preferences. Both physician fellows and attending physicians will be included as participants to ensure the recruitment goal of 20 is met for Study 2. We recognize that fellows are unlikely to have as much experience in patient communication as attending physicians, however, at our site, fellows often initiate difficult and advance care planning discussions given their primary roles in the cardiac intensive care unit. Others have included both fellows and attending physicians in their healthcare communication research.^{5,6}

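### Feasibility is part of the primary outcome, but the Analysis Plan specifies no analysis of it, and no record of eligible or approached patients is planned

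*Combined protocol and SAP*

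**What the plan says.** Study Aims sets the primary outcome: "The primary outcome of this pilot study is determining feasibility and acceptability". Better patient-centred communication and greater physician comfort are described there as aims for the future.

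Under Recruitment and Sample, "A total of 20 physicians will be recruited", 10 randomised to each arm. A new patient who meets the criteria "in any hospital setting (inpatient, outpatient cardiology clinic, emergency room) being cared for by a participating physician will be eligible for the study".

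Under Procedures, "Intervention arm physicians will participate in a 1-hour training". The intervention itself is a concrete event: "It involves the collaborative completion of a 2-page communication preferences document between a primary physician and an adolescent/young adult patient".

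Under Outcome Measures, the intervention-arm survey for physicians covers satisfaction and, as separate topics, "ease of intervention administration/completion, time to complete WE CHATT intervention with patient, barriers/feedback specific to WE CHATT", followed by knowledge gained and perceived impact. Patients and caregivers in that arm receive a matching survey.

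The Analysis Plan has three sentences. The first two apply paired t-tests (within the intervention arm) and ANCOVA (between arms) to physician comfort, patient/family satisfaction, trust and empathy. The third is the only descriptive analysis: "Frequencies, percentages and means will be calculated to describe physician, patient and family satisfaction with the WE CHATT intervention".

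**The concern.** In a feasibility pilot, the main result is whether the procedure can be carried out: whether physicians are trained, whether they use the tool, how many patients are reached, and whether the data come back. The plan names feasibility as primary and then specifies no quantity that would measure it. Two of its three analysis sentences concern measures that Study Aims does not make primary.

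Satisfaction cannot fill the gap, because the people best placed to rate WE CHATT are those who used it. A well-liked tool that reached most patients and a well-liked tool that reached few could give the same satisfaction percentages, yet they would lead to different decisions about a larger trial.

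There is also a matter of timing. A missing sentence about survey items can be added at any point before analysis. A missing record of who was eligible and who was approached may not be recoverable once the study has run.

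**Working it through.** The plan gives no feasibility target, power calculation or patient number, so there is no stated figure to reproduce beyond the allocation, which is consistent: 10 + 10 = 20. The main check sets the sections side by side.

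**Step 1. Is each feasibility-type quantity given an analysis?**

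- Ease, time to complete, barriers: collected under Outcome Measures from intervention-arm physicians and from patient/caregiver dyads. None is named in the three analysis sentences.
- Physicians trained: a training session is planned, but no attendance count.
- WE CHATT delivered: the completed document defines delivery, but no count or proportion is planned.
- Patients eligible, approached and consented: eligibility is defined, but no count or proportion is planned.
- Surveys returned: surveys are assigned, but no return proportion is planned.
- Satisfaction with WE CHATT (acceptability): named in the third analysis sentence.

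**Step 2. Which of these could be counted afterwards?** Completed documents and returned surveys are physical or electronic records and can be counted later if kept. Training attendance and enrolment can probably be recovered too. Patients who were eligible or approached but did not enrol are different. The only records review described is "Medical chart review will be completed to gather patient demographics and basic medical history, which will be used to define the study sample", and it serves the study sample. No screening log is mentioned, and eligible patients may appear in inpatient, outpatient or emergency settings.

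**Step 3. Can satisfaction stand in for delivery?** Take two hypothetical outcomes among the 10 intervention physicians (the counts are assumptions, not figures from the plan).

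- Case A: all 10 deliver WE CHATT and all are satisfied. Satisfaction = 10/10 = 100%. Delivery = 10/10 = 100%.
- Case B: 6 deliver and are satisfied; 4 do not deliver and leave the item blank. Satisfaction among respondents = 6/6 = 100%. Delivery = 6/10 = 60%.

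The planned summary reads 100% in both cases. Satisfaction and delivery are different quantities and both are legitimate. The point is that only the first is planned, and that the plan does not say how participants with no delivery enter it.

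**Step 4. What precision would a delivery proportion have?** The exact (Clopper–Pearson) 95% limits for x out of n are: lower = 0.025 quantile of Beta(x, n − x + 1); upper = 0.975 quantile of Beta(x + 1, n − x), with upper = 1 when x = n. With n = 10 physicians randomised to the arm:

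| Observed | Lower | Upper | Reported |
|---|---|---|---|
| 5/10 | 0.187 | 0.813 | 19–81% |
| 6/10 | 0.262 | 0.878 | 26–88% |
| 8/10 | 0.444 | 0.9748 | 44–97% |
| 10/10 | 0.692 | 1.000 | 69–100% |

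The same calculation cannot be done for patients or caregivers, because no patient number is stated.

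**The case against.** The best defence is that feasibility data are in the plan. Ease, time and barriers are listed as outcome measures, and the third analysis sentence names the same three groups who complete the WE CHATT survey, so it could be shorthand for the whole survey. This is possible but not the natural reading, because the survey description lists satisfaction separately from the other topics. Even if it were accepted, a survey does not count the patients who were eligible or approached, or the documents completed.

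A second defence is that much of this will be known anyway. The compensation section pays intervention physicians partly for attending training and engaging with patients, which suggests that some record will exist. Recruitment can be judged against the stated goal of 20 from 37 + 16 = 53 physicians. Both points stand, but neither is defined as an outcome. The recruitment statement is a planning argument about physicians, not a measure of delivery.

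A third is practical. Finding every eligible patient across several settings is real work, and intervals as wide as 44–97% with no progression threshold settle little. This also stands in part. It is why the log should record patients known to be eligible rather than claim full capture, and why the analysis should be descriptive.

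A reader might infer more than the text supports: that the investigators have ruled out analysing ease, time and barriers, or that all feasibility information will be lost. The documents specify no such analysis but do not exclude one, and only the eligible and approached counts are at clear risk. Nor does the 6/6 against 6/10 contrast show that the plan overstates satisfaction. It shows only that satisfaction and delivery must be reported together.

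**Conclusion.** The point holds. Feasibility is part of the primary outcome and no analysis of it is specified: three feasibility-type survey items have no stated summary, and no delivery, consent or survey-return proportion is planned. A team following the plan exactly would report satisfaction among respondents and nothing on how far the tool reached.

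This is a change the sponsor should make. It is not an error in any stated figure, and acceptability is adequately covered. The conclusion rests on reading satisfaction in the Analysis Plan as the survey topic of that name, and on the absence of any mention of a screening log. If an unpublished operating procedure already provides a log, what remains is to write the analyses into the plan.

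**What to change.** Keep a simple prospective log from the start and make the primary analysis descriptive, with fixed denominators:

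- (a) Intervention-arm physicians trained, and those delivering WE CHATT to at least one patient, each out of all randomised to that arm, with an exact 95% interval. Report separately the number who had no eligible patient.
- (b) Patients known to be eligible, approached and consented, by arm.
- (c) Completed WE CHATT documents out of enrolled intervention-arm patients, counting a patient without one as not delivered. Enrolled rather than eligible patients are the denominator, so that declining the research is not mixed with non-delivery.
- (d) Surveys returned out of those due, by arm and respondent type.

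Extend the descriptive sentence in the Analysis Plan to ease, time to complete and barriers. Report satisfaction with the number of respondents, beside the delivery counts.

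Label the t-tests and ANCOVA as secondary or exploratory. Physicians are the randomised units, so where a physician contributes more than one patient or dyad, between-arm patient and caregiver estimates should allow for clustering by physician.

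The cost is modest log-keeping and a few added sentences, with no extra participants or visits. Capture of eligible patients across settings may be incomplete and should be reported as such. The intervals will be wide, and the report should say so.

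### If physicians from both arms treat the same new patient, does the plan need a rule for which physician sets that patient's arm?

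*Combined protocol and SAP*

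**What the plan says.** Under Methods, Recruitment and Sample (Physicians), the physician is the unit of allocation: "10 will be randomized to participate in the intervention arm and 10 will be randomized to the control arm". The recruiting division is "currently comprised of 37 attending physicians and 16 fellows". The Limitations section confirms that both ranks may enrol.

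Under Patient/Caregivers, a new patient aged 12 to 24 with NYHA Class II to IV symptoms is eligible when "meeting the above criteria in any hospital setting (inpatient, outpatient cardiology clinic, emergency room) being cared for by a participating physician".

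Under Procedures, the arms differ by training. For the intervention, "Intervention arm physicians will participate in a 1-hour training"; for control, "Physicians randomized to the control arm will not receive training in the WE CHATT communication intervention". The tool is a "2-page communication preferences document between a primary physician and an adolescent/young adult patient". Among the Patient/Caregiver Measures, the intervention-arm survey asks about "time to complete WE CHATT intervention with physician", in the singular.

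The Analysis Plan compares the groups by ANCOVA on physician comfort and on patient and family satisfaction, trust and perceived empathy. Study Aims sets the priority: "The primary outcome of this pilot study is determining feasibility and acceptability".

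**The concern.** Physicians are randomised and patients are not, so a patient has an arm only through a link to a physician. The one link in the text is care by a participating physician, in any hospital setting. An inpatient might be seen by a fellow and an attending, both enrolled and in different arms. The protocol does not say which of them counts. New patient and primary physician are undefined, and the second term appears only in the description of the intervention. The physician to be rated on PediTIPS and CARE is not named either.

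Trained physicians know their arm. If care were shared, whoever made the link could know the allocation, and patients expected to give warm ratings could drift towards one arm. That would bias the between-arm comparisons of satisfaction, trust and empathy, in either direction.

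**Working it through.** The plan gives no power, effect size or patient number, so there is no stated figure to reproduce. The check has two parts.

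**1. The wording.** Eligibility runs through a participating physician. The tool is completed by one primary physician with one patient. The compensation paragraph pays intervention physicians for delivering the intervention to patient participants. The survey items refer to the physician in the singular. Taken together, a patient enters through one participating physician and takes that physician's arm. What is missing is a tie-break for overlaps.

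**2. The size of the gap, as an illustration.**

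Inputs from the protocol: 37 + 16 = 53 division physicians, of whom 10 are intervention, 10 control and 53 − 20 = 33 non-participating.

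Assumed inputs, not in the documents: k treating division physicians per patient, drawn at random from the 53; half of shared patients rate d = 0.5 SD above the other half; a fraction q of the higher raters is linked to one arm and the same fraction of the lower raters to the other; arms of equal size; no covariate adjustment.

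Share of eligible patients seen by both arms:

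s = [C(53,k) − 2·C(43,k) + C(33,k)] / [C(53,k) − C(33,k)]

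- k = 1: 0.
- k = 2: (1378 − 1806 + 528)/(1378 − 528) = 100/850 = 0.118.
- k = 3: (23426 − 24682 + 5456)/(23426 − 5456) = 4200/17970 = 0.234.
- k = 4: (292825 − 246820 + 40920)/(292825 − 40920) = 86925/251905 = 0.345.

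If each patient instead has exactly one fellow and one attending, with f fellows enrolled and allocation not stratified by rank:

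s = (f/16)·((20 − f)/37)·(10/19) / [1 − (1 − f/16)(1 − (20 − f)/37)]

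This is 0 at f = 0, peaks at 0.0853/0.6622 = 0.129 at f = 8, and is 0.057 at f = 16.

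Shift in the between-arm difference = s·d·(2q − 1):

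| k | s | q = 0.5 | q = 0.75 | q = 1 |
|---|---|---|---|---|
| 1 | 0 | 0 | 0 | 0 |
| 2 | 0.118 | 0 | 0.03 SD | 0.06 SD |
| 3 | 0.234 | 0 | 0.06 SD | 0.12 SD |
| 4 | 0.345 | 0 | 0.09 SD | 0.17 SD |

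The shift is proportional to d. It is zero when the link is made without regard to arm.

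For scale, the standard error of a difference in means, ignoring clustering by physician, is √(2/n) SD with n patients per arm. Patient numbers are not given. Assuming n = 10, 20 or 30, it is 0.45, 0.32 or 0.26 SD. The nonzero shifts at q = 0.75 then run from 0.029/0.447 = 7% to 0.086/0.258 = 33% of one standard error. The extreme cell, 0.173/0.258, is 67% at n = 30. Positive clustering by physician would raise the standard errors and lower these percentages.

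**The case for a change.** The strongest case for a change is that the protocol does plan these between-arm comparisons and that a link made with allocation known is hard to repair later, so a rule should exist before patients are approached. Primary physician describes the tool, has no counterpart in the control arm and is not an arm-assignment rule. The Limitations section gives fellows primary roles in the cardiac intensive care unit, so for an inpatient the term could mean the fellow or the attending. A rule would cost a few sentences.

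Part of this stands. The documents contain no tie-break, and staff will have to know which physician a survey refers to.

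The rest carries less weight. No passage shows that participants from opposite arms treat the same study patient. The PediTIPS and CARE forms are not in the documents and may already name the physician. Analysis is not helpless either: in the model above all the bias comes from shared patients, so if overlap is recorded, a sensitivity analysis without them has no expected shift.

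A written rule can also do harm. Setting the index physician by first encounter or by a random list, and treating that person as the primary physician, could hand the tool to someone with only brief contact. That would change who delivers the intervention, and so touch the feasibility and acceptability that the pilot exists to measure. Such a rule would also rest on the first new-patient encounter while new patient stays undefined.

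**Conclusion.** No change to the plan is needed. This is an undefined term that a study team fills sensibly: one physician per patient, that physician's randomised arm, and surveys about that physician. Noting the physician at enrolment, in the same way in both arms, is ordinary study conduct.

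The possible bias is 0 to 0.09 SD under 75% selective linking and up to 0.17 SD in the worst case shown. Both figures rest on an assumed number of treating physicians, random mixing within the division, and an assumed 0.5 SD gap between higher and lower raters. Cross-arm care and selective linking would both have to occur, and neither is documented. With one treating division physician, or with linking that ignores arm, the expected shift is zero.

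The exposure is confined to secondary patient and caregiver comparisons in a 20-physician pilot. Physician comfort is compared in the arms as randomised, and the primary outcome is little affected. Contamination from shared care is a separate matter that an index-physician rule would not remove. The conclusion would be weaker if patients were commonly treated by four or more division physicians and the link were left to staff who favoured one arm; nothing in the protocol suggests this.
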